## 9.7.3 Demographics and Other Baseline Characteristics

Demographic parameters (eg, age, race, ethnicity, sex, weight, height, body mass index [BMI]) and other baseline characteristics will be summarized by treatment group for the Safety and *m*ITT populations.

# 9.7.4 Extent of Exposure and Treatment Compliance

#### 9.7.4.1 Extent of Exposure

Patients in the Safety Population will be categorized by the number of IP doses received. The number and percentage of patients in each category will be summarized by treatment group.

*Prior medication* is defined as any medication taken before the date of the first dose of randomized IP. *Concomitant medication* is defined as any medication taken on or after the date of the first dose of randomized IP.

Both prior and concomitant medication use will be summarized by the number and proportion of patients in each treatment group receiving each medication within each therapeutic class for the Safety Population. Multiple medication use by a patient will only be counted once.

IV administration notes including site reaction at placement of IV, reaction to adhesive, infusion interruption, failure of administration device, increase in suicidality based on clinical evaluation, and perceptual disturbance based on mental status assessment are collected. For each item, the number and percentage of patients who had a 'yes' response will be summarized by treatment group and visit for the Safety Population. The number and percentage of patients taking each qualifying ADT will be summarized by treatment group for the mITT Population. Mean daily dose for each qualifying ADT will be summarized using descriptive statistics (number of patients, mean, standard deviation [SD], median, Q1, Q3, minimum, and maximum) by treatment group for the mITT Population.

## 9.7.4.2 Measurement of Treatment Compliance

Dosing compliance for the background ADT during a specified period is defined as the total daily dose administered to a patient during that period divided by the total daily dose prescribed during the same period multiplied by 100, as captured in the eCRF. Descriptive statistics for ADT compliance will be presented for each ADT and overall by treatment group for the mITT Population.

## 9.7.5 Efficacy Analyses

All efficacy analyses will be based on the *m*ITT Population, unless stated otherwise. The baseline for each specific efficacy endpoint is defined as the last measurement prior to the first dose of randomized treatment. All statistical hypothesis tests will be performed at the 2-sided 5% significance level for main effects. All confidence intervals (CIs) will be 2-sided 95% CIs, unless stated otherwise.

For efficacy analyses in which study center is a factor, a small center will be defined as a center with < 2 patients in  $\ge 1$  treatment group in the mITT Population. Small centers will be pooled to form pseudo-centers so that each treatment group includes  $\ge 2$  mITT patients within the center. Details of the pooling algorithm will be provided in the Statistical Analysis Plan (SAP).

## 9.7.5.1 Primary Efficacy Parameter

The primary efficacy parameter will be the change from baseline in MADRS total score at end of study. The primary analysis will be performed using a mixed-effects model for repeated measures (MMRM) with treatment group, pooled study center, visit and randomized treatment-by-visit interaction as the fixed effects, and baseline MADRS total score and baseline MADRS total score-by-visit interaction as covariates. An unstructured covariance matrix will be used to model the covariance of within-patient scores. The Kenward-Roger approximation will be used to estimate the denominator degrees of freedom (Kenward et al, 1997; Kenward et al, 2003). The treatment difference for rapastinel doses versus placebo will be estimated and reported along with the corresponding 95% CI and nominal p-value.

In the case that the MMRM model with unstructured covariance fails to converge with the default algorithm, then the Fisher scoring algorithm will be used to provide better initial values of the covariance parameters; if the model still does not converge, a simplified model without term for study center will be used to find the initial values of the covariance parameters. In the rare event that the model still does not converge after using those initial values, simplified covariance structures will be used to fit the model in the following order: (1) ante-dependence, (2) heterogeneous autoregressive, (3) Toeplitz, and (4) compound symmetry.

[figure not shown]
To assess the robustness of the primary MMRM results to the possible violation of the missing-at-random assumption, a sensitivity analysis using a pattern-mixture model based on non-future dependent missing value restrictions (Kenward et al, 2003) will be performed. The pattern for the pattern-mixture model will be defined by the patient's last visit with observed value. The observed MADRS total score at a visit is assumed to have a linear relationship with the patient's prior measurements. The missing values will be imputed under the assumption that the distribution of the missing observations differs from the observed only by a shift parameter value  $\Delta$ . The dataset with missing values will be analyzed using the same model as the primary analysis for betweentreatment group comparisons at the end of the treatment. The imputation of missing values and the analysis will be performed multiple times and the inference of this sensitivity analysis will be based on the combined estimates using the standard multiple imputation technique. The values of  $\Delta$  will be selected as 0 to 8.

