## 9.7.5.2 Key Secondary Efficacy Parameter

The key secondary efficacy parameter will be the change from baseline to 1 day after the first dose of treatment in MADRS total score. This parameter will be analyzed using the same MMRM as will be used for the primary efficacy parameter. The treatment difference for rapastinel versus placebo will be estimated and reported along with the corresponding 95% CI and nominal p-value.

A sequential testing procedure will be used to control the overall type I error rate at 5% for the comparisons of treatment difference in the following order:

- Rapastinel 450 mg versus placebo primary efficacy parameter
- Rapastinel 450 mg versus placebo key secondary efficacy parameter
- Rapastinel 225 mg versus placebo primary efficacy parameter
- Rapastinel 225 mg versus placebo key secondary efficacy parameter

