## 9.7.8 Interim Analysis

At the time of preparation for Protocol Amendment 2, a blinded interim analysis was performed as part of data quality review as the study was progressing. In this review, it was observed that the SD for the primary and secondary endpoints were substantially lower than the originally assumed values for sample size calculations. The observed SDs in the blinded reviews of this study and other ongoing acute studies at the same time (RAP-MD-02 and RAP-MD-03) were taken into consideration for revising the estimate of the sample size as proposed in the next section (Section 9.7.9 Determination of Sample Size).

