### 9.7.9 Determination of Sample Size

The originally proposed primary efficacy variable is the change from baseline in the MADRS total score at 1 day after the first dose of treatment. The study was planned to randomize 1050 patients assuming SD of 10 points, which provides 99% power to detect a difference of 3.25 points in MADRS total score between at least 1 of the 2 rapastinel dose groups and placebo at a 2-sided significance level of 0.05.

While the study was ongoing, the primary efficacy variable was revised to be the change from baseline in MADRS score at the last visit, Day 21, as recommended by the FDA, EMA, and PDMA, and included in Amendment 2 of the protocol. At the same time of Amendment 2, a blinded data review was conducted for Studies RAP-MD-01, RAP-MD-02, and RAP-MD-03. The pooled SD for the 3 studies were 7.4, 8.0, and 8.7, respectively, all smaller than the originally assumed 10 points. Sample size was recalculated using 8.7 as the common SD. The calculation used MMRM model with simulations; it also assumed correlation of 0.5 between the repeated measures and an overall dropout rate of 15%. To have 90% power, the total sample size required is 540 patients. However, the study had already enrolled more than 590 patients with less than 5% of overall dropout rate, surpassing the re-estimated sample size of 540 patients. The study enrollment will be halted as soon as operationally feasible. The final sample size expected is approximately 630 patients (210 patients per treatment group).

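### The last two fallback covariance structures (Toeplitz, compound symmetry) impose one variance on all visits with only Kenward-Roger inference, so if they are reached and visit variances differ, the Day 21 or Day 1 test can exceed 5%

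*Protocol*

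**What the plan says.** Section 9.7.5.1 makes an MMRM with unstructured covariance the primary analysis and adds: "The Kenward-Roger approximation will be used to estimate the denominator degrees of freedom". If the fit fails, Fisher scoring is tried, then starting values from a model without study center. Should that fail too, which the protocol regards as unlikely, simpler forms replace the unstructured matrix: "covariance structures will be used to fit the model in the following order: (1) ante-dependence, (2) heterogeneous autoregressive, (3) Toeplitz, and (4) compound symmetry". Only the second structure is called heterogeneous. No robust standard error is stated for any of the four.

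Section 9.7.5.2 covers the change in MADRS at 1 day after the first dose: "This parameter will be analyzed using the same MMRM as will be used for the primary efficacy parameter". It also sets a fixed testing sequence meant to hold the overall type I error at 5%. The first test is 450 mg at the end of study (Day 21) and the second is 450 mg at Day 1.

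On variability, Section 9.7.8 reports that in blinded review "it was observed that the SD for the primary and secondary endpoints were substantially lower than the originally assumed values". Section 9.7.9 gives one pooled SD per study (7.4, 8.0 and 8.7) and states: "Sample size was recalculated using 8.7 as the common SD". No SD is given by visit.

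**The concern.** Unstructured, ante-dependence and heterogeneous autoregressive covariances each estimate a separate variance at every visit. Toeplitz and compound symmetry, in their standard forms, estimate one variance for all visits. The confirmatory contrasts are single-visit comparisons, so under the last two structures their standard errors come from an average variance, not from the variance at the visit tested. Kenward-Roger is a small-sample adjustment that takes the chosen structure as correct, so it leaves this error in place.

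A visit with above-average variance is then tested too liberally and a visit with below-average variance too conservatively. If SDs rise over the three weeks, the inflated test is the Day 21 primary, which opens the sequence. If they fall, it is the Day 1 key secondary. Either way, the 5% control claimed in Section 9.7.5.2 would not hold in that branch.

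**Working it through.** **The plan's own figures.** With 350 per arm, SD 10 and a 3.25-point difference, 3.25/(10 × √(2/350)) − 1.96 = 2.34, so power is 99.0% (stated 99%). For the re-estimate, with 3.25 assumed to carry over, n = 2 × (1.96 + 1.2816)² × (8.7/3.25)² = 151 per arm. Then 151/0.85 = 178 per arm, or 534 in total (stated 540). Both reproduce. For the 5% type I error under the fallback the protocol gives no calculation.

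**Inputs.**
- Nine post-dose visits, on Days 1, 4, 7, 8, 11, 14, 15, 18 and 21. This follows from the visit pattern in Section 9.1.2 and the statement in Section 9.2 that efficacy is assessed at every visit.
- Correlation 0.5 between visits (Section 9.7.9).
- By-visit SDs: all assumed, linear in day. The values 7.4 and 8.7 also appear in Section 9.7.9 as per-study SDs, which is not evidence of a trend over visits.

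**Formula.** With balanced data, the common variance fitted by compound symmetry is the mean of the visit variances. Let r = √(fitted variance / true variance) at the tested visit. Then type I error = 2 × (1 − Φ(1.96 r)).

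**Worked example, SD 7.4 to 8.7.** The mean day is 11, and the mean squared deviation of the days is 348/9 = 38.67. The SD slope is 1.3/20 = 0.065 per day and the mean SD is 8.05. Mean variance = 8.05² + 0.065² × 38.67 = 64.97, so the pooled SD is 8.06.
- Day 21: r = 8.06/8.7 = 0.926, type I error 6.9%.
- Day 1: r = 8.06/7.4 = 1.089, type I error 3.3%.

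**Compound symmetry, other paths.**

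| SD, Day 1 to Day 21 | r, Day 21 / Day 1 | Type I error, Day 21 / Day 1 |
|---|---|---|
| 7.4 to 8.7 | 0.926 / 1.089 | 6.9% / 3.3% |
| 6.5 to 8.7 | 0.877 / 1.174 | 8.6% / 2.1% |
| 6 to 9 | 0.840 / 1.260 | 10.0% / 1.4% |
| constant 8.7 | 1.000 / 1.000 | 5.0% / 5.0% |
| 9.5 to 8.7 | 1.046 / 0.958 | 4.0% / 6.0% |
| 8.7 to 7 | 1.124 / 0.904 | 2.8% / 7.6% |

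Toeplitz is within 0.2 points of these. A U-shaped path (8.7, 7.4, 8.7, turning at Day 11) gives 6.8% on both days. A hump (7.4, 8.7, 7.4) gives 3.4% on both. Heterogeneous autoregressive gives 5.0% throughout.

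**Simulation with dropout.** Three arms of 210, correlation 0.5, 40 pooled centers (number assumed), monotone dropout dependent on the last score, 2,500 runs and two dose contrasts per case, Monte Carlo SE about 0.3 points. Compound symmetry was fitted by generalised least squares with moment estimates. Results at 5% dropout, model-based / sandwich:

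| SD path | Day 21 | Day 1 |
|---|---|---|
| 7.4 to 8.7 | 7.1 / 5.2% | 3.6 / 5.8% |
| 6.5 to 8.7 | 8.0 / 5.1% | 2.6 / 5.0% |
| 6 to 9 | 10.6 / 5.6% | 1.7 / 5.8% |
| constant 8.7 | 5.0 / 5.2% | 5.6 / 5.8% |
| 9.5 to 8.7 | 4.3 / 5.6% | 6.7 / 5.7% |
| 8.7 to 7 | 3.2 / 5.4% | 7.9 / 5.6% |

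Over dropout of 5% and 15% and both days (24 results), the sandwich gave 4.6–6.1%, averaging about 5.5%.

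**Cross-check.** A separate simulation of 20,000 complete-data trials at 210 per arm, SD 7.4 to 8.7, gave 7.0% (Day 21) and 3.5% (Day 1) under compound symmetry. With a separate variance per visit it gave 5.1% and 5.2%.

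**The case against.** The strongest objection is that the branch is practically unreachable. The default algorithm, Fisher scoring, center-free starting values, ante-dependence and heterogeneous autoregressive must all fail first, with about 630 patients and under 5% dropout. In 240 simulated data sets of this shape the unstructured model converged every time, although by an EM-type maximum-likelihood algorithm and not SAS REML. If the last two structures were reached in 1% of trials (an assumed rate), a 6.9% test adds 0.01 × 1.9 = 0.02 points to the overall type I error, and a 10.6% test adds 0.06. This stands, and it is why the point is minor.

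The by-visit SDs are also assumed, the direction is unknown, and a mid-study peak makes both tests conservative. That stands too.

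It can be said that standard errors for a last-resort structure belong in the SAP, which was not available for this check. That does not dispose of the point: the protocol itself fixes the order and the inference method, and their combination is what fails. It can also be said that ante-dependence carries no heterogeneous label yet has visit-specific variances, so the missing word proves little. That is fair as far as it goes, but the conventional meaning of Toeplitz and compound symmetry is a single variance.

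Finally, the remedies are imperfect. The sandwich raises the error on the conservative paths and is slightly liberal overall. Raising a 1.7% test towards 5% restores the nominal level, but the residual liberality is real. The dropout simulation did not use the protocol's likelihood fit with Kenward-Roger, so its tenths of a point should not be over-read.

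**Conclusion.** The point holds, conditionally and at low severity. If Toeplitz or compound symmetry is reached and visit variances differ, the stated inference does not give a 5% test at each of Day 21 and Day 1. For the assumed monotone paths, the inflated test runs at about 6% to 10%, while the other falls below 5%. With equal SDs and correlation 0.5 there is no error. The main analysis and the first two fallback structures are not affected in this way.

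The conclusion rests on reading the two structures in their standard single-variance forms, on assumed by-visit SDs, and on MADRS being rated at all nine post-dose visits. Which of the two tests would be inflated cannot be determined from the protocol.

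**What to change.** Keep the order and add one sentence to Section 9.7.5.1:

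> If Toeplitz or compound symmetry is used, standard errors and tests will use the empirical (sandwich) estimator with between-within degrees of freedom; Kenward-Roger is kept for the unstructured model, ante-dependence and heterogeneous autoregressive.

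This costs one sentence and two SAS options. The sandwich does not remove bias from a wrong covariance combined with dropout. In simulation the Day 21 estimate shifted by at most 0.08 points of a 3.25-point effect, close to Monte Carlo noise.

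The alternative is to name the heterogeneous versions of Toeplitz and compound symmetry and keep Kenward-Roger. With nine visits these have 17 and 10 covariance parameters, the same as ante-dependence and heterogeneous autoregressive, which would already have failed. The plain versions have 9 and 2. Heterogeneous compound symmetry is also conservative (3.8% on both days) if correlation decays as 0.9 to the power of the lag. The sandwich sentence is therefore the better choice.

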## 9.7.5.2 Key Secondary Efficacy Parameter

The key secondary efficacy parameter will be the change from baseline to 1 day after the first dose of treatment in MADRS total score. This parameter will be analyzed using the same MMRM as will be used for the primary efficacy parameter. The treatment difference for rapastinel versus placebo will be estimated and reported along with the corresponding 95% CI and nominal p-value.

A sequential testing procedure will be used to control the overall type I error rate at 5% for the comparisons of treatment difference in the following order:

- Rapastinel 450 mg versus placebo primary efficacy parameter
- Rapastinel 450 mg versus placebo key secondary efficacy parameter
- Rapastinel 225 mg versus placebo primary efficacy parameter
- Rapastinel 225 mg versus placebo key secondary efficacy parameter

# 9.7.6.1 Adverse Events

AEs will be coded by system organ class and preferred term using the *Medical Dictionary for Regulatory Activities*.

An AE (classified by preferred term) will be considered a treatment-emergent adverse event (TEAE) if it was not present before the first dose of IP or was present before the date of the first dose of IP and increased in severity after the first dose of IP. An AE that becomes serious after the date of first dose of IP will also be considered as a TEAE. If more than 1 AE is reported before the first dose of IP and coded to the same preferred term, the AE with the greatest severity will be used for comparison with the AEs occurring during the double-blind treatment period that were also coded to that preferred term. An AE that occurs more than 30 days after the date of the last dose of IP will not be considered as a TEAE.

The number and percentage of patients reporting TEAEs in each treatment group will be tabulated by system organ class and preferred term and further categorized by severity and causal relationship to the IP. If more than 1 AE is coded to the same preferred term for the same patient, the patient will be counted only once for that preferred term using the greatest severity and strictest causality for the summarization by severity and causal relationship.

A serious adverse event (SAE) that occurred between the date of the first dose of IP and 30 days after the date of the last dose of IP, inclusive, will be considered a treatment-emergent SAE (TESAE). The number and percentage of patients who have TESAEs will be summarized by preferred term and treatment group. In addition, the incidence of TESAEs that lead to death will be summarized separately by preferred term for each treatment group.

Overall summaries of AEs will be provided on a per-patient basis for categories of all TEAEs, treatment-related TEAEs, TESAEs, and TEAEs leading to study discontinuation.

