#### 9.4.2 Treatments Administered

The IP will only be administered to eligible patients by a medically qualified person as per the local state regulations. The range of persons who can administer an IV can be a physician, a physician assistant, nurse, or nurse practitioner, etc, depending on the local and/or state law.

IP should be administered after all efficacy and safety assessments with the exception of the post-dose assessments described below. IP will be administered in a "slow bolus" injection to each study patient in an upper extremity vein within approximately 1 to 2 minutes.

[figure not shown]
During IP administration and until completion of postadministration assessments a licensed physician must be immediately available and in close proximity to the patient(s) to attend to medical emergencies. The study center must have the capabilities, in accordance with the applicable country, local, and/or state regulations and standard of care, to resuscitate a patient in the event of a medical emergency.

The patient should not be discharged from the study center until the following are completed:

- Postadministration vital sign measures (approximately 15 minutes after administration)
- Patient is clinically assessed and determined to not be at increased risk of suicidality in the opinion of the Investigator (or medically qualified subinvestigator)

- Patient is assessed for mental status and is determined to be free of perceptual disturbances or other conditions that would deem them not ready for discharge from the study center, in the opinion of the Investigator (or medically qualified subinvestigator)
- A physician licensed in the state (Investigator or subinvestigator) determines that they are medically able to leave the study center and provides written sign-off not less than 15 minutes following administration (see IV Administration and Discharge Notes document in Program Reference Manual)

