#### 9.5.2.1 Adverse Events

An AE is any untoward medical occurrence in a patient or clinical investigation patient administered a pharmaceutical product and which does not necessarily have to have a causal relationship with this treatment. An AE can therefore be any unfavorable and unintended sign (including an abnormal laboratory finding, for example), symptom, or disease temporally associated with the use of a medicinal product, whether or not considered related to the medicinal product (ICH-E2A).

For the purpose of the study center's data collection responsibilities, any untoward event that was reported from the time the patient signed the ICF until 30 days after the final protocol-defined study visit or the last known dose of IP (if the final visit does not occur) is to be considered an AE.

Examples of AEs are as follows:

- Changes in the general condition of the patient
- Subjective symptoms offered by or elicited from the patient
- Objective signs observed by the Investigator or other study center personnel
- All diseases that occur after signing informed consent, including any change in severity or frequency of pre-existing disease
- All clinically relevant abnormalities in laboratory values or clinically relevant physical findings that occur during the study schedule

Please note that medical procedures scheduled prior to consenting, but occurring during the study should not be captured as AEs, but should be listed in the medical history if related to a pre-existing condition.

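### The TEAE definition mixes the time and the date of the first dose, so some events that worsen or become serious on the first dosing day are not counted as TEAEs

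*Protocol*

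**What the plan says.** Protocol section 9.7.6.1 classifies AEs by preferred term and gives three routes to TEAE status.

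- **Routes 1 and 2.** An AE qualifies "if it was not present before the first dose of IP or was present before the date of the first dose of IP"; in the second case it must also have worsened once dosing had begun. Route 1 therefore turns on the dose and route 2 on the date of the dose.
- **Route 3.** "An AE that becomes serious after the date of first dose of IP will also be considered as a TEAE".

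If a term was reported more than once before the first dose, "the AE with the greatest severity will be used for comparison with the AEs occurring during the double-blind treatment period". The same section defines a TESAE by calendar date, from the day of the first dose to 30 days after the last, both ends included. It then lists TEAEs and TESAEs together in the overall per-patient summary.

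Two other sections set the pre-dose period. Section 9.5.2.1 counts as an AE "any untoward event that was reported from the time the patient signed the ICF", and section 9.1.1 allows up to 14 days of screening. Section 9.4.2 states that "IP should be administered after all efficacy and safety assessments", apart from the post-dose checks. Section 9.4.7.2 puts the first dose on the Baseline visit day. That day therefore has a stretch before the injection in which an AE can begin.

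**The concern.** Two matters arise, of different weight.

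The first is a drafting error. Routes 1 and 2 are meant to divide all AEs between terms new since dosing and terms already there that got worse. Because one uses the dose and the other its date, events that begin on the dosing day before the injection fall between them. Route 3 and the TESAE window also treat the dosing day differently: one starts after it, the other includes it. Followed literally, the rule leaves an on-treatment worsening out of the TEAE tables, and a patient can appear under TESAEs without appearing under TEAEs.

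The second is a choice of convention. The reference for worsening is anything reported under the same preferred term since consent, and nothing limits it to events still ongoing at the first dose. A new episode after an injection can then be left out because a similar one occurred, and ended, in screening. This affects the all-TEAE, treatment-related and discontinuation summaries.

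**Working it through.** The plan states no figure on this point, so there is none to reproduce. The check applies the three routes literally to each case. Day 1 is the date of the first dose.

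| Case | Route 1: term absent before the dose | Route 2: present before the date, and worse | Route 3: serious after the date | TEAE? | In TESAE window? |
|---|---|---|---|---|---|
| A. Term first appears after the injection, Day 1 included | yes | – | – | yes | if serious |
| B. Starts on Day 1 before the injection, worsens after it | no | no (not before the date) | no | **no** | not serious |
| C. As B, and becomes serious later on Day 1 | no | no | no | **no** | **yes** |
| D. Term present in screening, no worsening, becomes serious on Day 1 after the injection | no | no | no | **no** | **yes** |
| E. As D, but becomes serious after Day 1 | no | no | yes | yes | yes |
| F. Term seen and resolved in screening; new episode more severe | no | yes | no | yes | if serious |
| G. As F, but new episode equally or less severe and not serious | no | no | no | **no** | not serious |

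Case B is the gap between routes 1 and 2. Cases C and D show that TESAEs need not be a subset of TEAEs. Case G is the preferred-term convention. With one pre-dose report, G follows from the definition itself. The sentence on greatest severity matters only when there were several. Severity has three levels (section 9.5.2.1.2), so after a severe screening episode only route 3 remains open for that term.

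**Size of case G, on assumptions.** The protocol gives no AE rates. The only documented input is 210 patients per group (section 9.7.9). Assumed values are a post-dose incidence of 10% in one arm and 5% in another; s, the share of patients with a post-dose episode who had the same term in screening, from 2% to 20%; and q, the share of those whose new episode is not more severe, from 60% to 90%.

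Patients lost = 210 × incidence × s × q.

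- At 10% (21 patients): 210 × 0.10 × 0.02 × 0.6 = 0.3, up to 210 × 0.10 × 0.20 × 0.9 = 3.8.
- At 5% (10.5 patients): 210 × 0.05 × 0.02 × 0.6 = 0.1, up to 210 × 0.05 × 0.20 × 0.9 = 1.9.
- Difference between arms = 5.0 × (1 − s × q): from 5.0 × 0.988 = 4.9 points to 5.0 × 0.82 = 4.1 points. The ratio of incidences stays at 2, because both arms are multiplied by the same factor.

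Other inputs give other answers. Let a share p of all patients have the term in screening, with later incidence r1 in them and r0 in the rest. The share lost is p·r1·q / (p·r1 + (1 − p)·r0).

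- p = 0.03, r1 = 0.2, r0 = 0.10, q = 0.7: 0.0042 / 0.103 = 4.1%.
- p = 0.05, r1 = 0.2, r0 = 0.10, q = 0.9: 0.009 / 0.105 = 8.6%.
- p = 0.10, r1 = 0.4, r0 = 0.05, q = 0.9: 0.036 / 0.085 = 42.4%.

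The last set assumes recurrence at eight times the rate in other patients. The spread shows that the inputs, not the document, decide the result. Cases B to D cannot be sized at all.

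**The case against.** Comparison with the worst pre-dose severity is a coherent rule, applied without regard to treatment, and its purpose is to separate background symptoms from new ones. Screening precedes randomisation, so earlier episodes are balanced between arms in expectation. If the drug makes episodes more severe, the rule keeps them. This stands, and it is why the convention itself is not called an error.

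Many of the events also appear elsewhere. All AEs are recorded in the eCRF (section 9.5.2.1.4). Section 9.7.2 tabulates reasons for discontinuation, of which AE is one. Section 9.7.4.1 tabulates site reactions, infusion interruption, increased suicidality and perceptual disturbance by visit, without regard to TEAE status. Some safety sections are not visible in the public text, so further analyses cannot be assumed absent.

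The gap on the dosing day can be called a stray word whose intent is clear, and the handling of onset times may be left to the SAP. This stands only in part. The protocol itself fixes the rule, and a SAP that follows it literally inherits the gap.

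A reader might infer three stronger points that the text does not support.

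- **Every recurrence of a screening term is dropped.** It is not: cases E and F are kept.
- **First-day reactions in general are missed.** They are not: a term that first appears after the injection is a TEAE (case A).
- **Serious events are lost.** They are not: cases C and D remain in the TESAE table.

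**Conclusion.** The mixed start points are wrong as written. Case B is left out although the event worsened after the injection, and cases C and D break the expected nesting of TESAEs within TEAEs. Each needs a particular coincidence on a single day, so few patients are likely to be involved, though the protocol gives no figures to confirm this.

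The preferred-term comparison is a defensible convention with a known cost: recurrences that are neither more severe nor serious are left out, even when the screening episode had ended. That resolved episodes count is inferred from the preferred-term matching and the absence of any requirement that they be ongoing; the section does not say so outright. The effect is probably modest (0.3 to 3.8 of 21 patients on the first set of assumptions), but it cannot be sized from the document. A claim of a large undercount, or of a bias that always favours the drug, would rest on assumed rates alone. With equal s and q, the absolute difference between arms shrinks somewhat and the ratio does not change.

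**What to change.** 1. Use the first dose, not its date, as the single start point throughout section 9.7.6.1. In substance, a TEAE is an AE whose preferred term was absent before the first dose, or was present before it and then worsened or became serious at or after it. The existing limit of 30 days after the last dose stays.
2. Start the TESAE window at the first dose as well, and state that every TESAE counts as a TEAE.
3. Keep the preferred-term comparison for the main tables if the sponsor prefers it. Add one supplementary table by arm counting every AE with onset at or after the first dose, whatever was reported in screening. It will show whether the convention matters.

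Items 1 and 2 are wording and a small change to the derivation, to be settled before unblinding. Section 9.4.12 already captures the date and time of each injection. AE onset on Day 1 must be recorded as before or after the injection, or a rule fixed for unknown times. Item 3 costs one extra table.
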